3. OBJECTIVE AND OUTCOME MEASURES

Aim 1: Identify the correlations between transdermal alcohol concentration (TAC) and breath alcohol concentration (BrAC) in controlled laboratory and natural settings and compare correlations across settings.

- Outcomes measures: BrAC using the BACtrack S80 and TAC readings using the BACtrack Skyn monitor and light-based finger monitor during laboratory alcohol drinking sessions and a remote assessment period.

Aim 2: Compare TAC and BrAC as predictors of self-reported number of drinks consumed and the odds and frequency of alcohol-related harms in natural settings.

- Outcome measures: BrAC and TAC readings, self-reported number of drinks and alcohol related harms measured using a mobile app questionnaire (LifeData app).

Aim 3: Model individual differences in alcohol-specific satiety using self-report and a paced-drinking alcohol administration laboratory model.

- Outcome measures: Alcohol specific satiety questionnaire, BrAC readings.
- Secondary measures: Self-report alcohol subjective effects (stimulation, sedation, craving), behavioral economic demand for alcohol, attentional bias for alcohol related cues.

Aim 4: Assess the effect of a dietary supplement on satiety to alcohol

- Outcome measures: Blood plasma GLP-1 levels samples during lab sessions via venipuncture before and after supplement administration, alcohol-specific satiety questionnaire

Aim 5: Assess the effect of alcohol exposure on HMBG-1 marker of inflammation

- Outcome measures: Blood plasma levels of HMBG-1 will sampled during lab sessions via fingerprick at timepoints before alcohol administration, 30 minutes after an initial priming drink, and after the final drink.

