Blood sampling: Blood is sampled at baseline and again 45 minutes after dietary supplement administration to assess the effect of the dietary manipulation on circulating GLP-1. Blood samples will be immediately placed on dry ice and centrifuged the same day. Extracted plasma will be stored at -80° C. Blood samples will be collected in a 2mL vacutainer pretreated with a DPP-4 inhibitor in accordance with manufacturer guidelines (EMD Millipore Corp., Billerica, MA). Only biologically active forms of GLP-1 will be measured which include GLP-1(7–36) and GLP-1(7–37) [74]. Blood samples will be processed in duplicate with the MILLIPORE Glucagon-Like Peptide-1 (Active) ELISA kit - 96-Well Plate (Cat. #EGLP-35K). HMGB-1 will be measured at three timepoints via a fingerprick blood sample. Plasma samples will be processed in duplicate using a deproteinization kit and the HMGB1 ELISA kit - 96-Well Plate (Cat. # EEL047).

Dietary supplements: commercially available supplements will be used to stimulate glp-1; 10g prebiotic fiber (digestive resistant maltodextrin; fibersol®-2) and 725mg decaffeinated green tea extract (<https://www.vitaminshoppe.com/p/triple-strength-green-tea-extract-100-vegetarian-capsules/vs-1807>). Dietary fiber [54, 55, 75-77] and green tea extracts [78, 79] separately have been shown to increase plasma levels of active glp-1 in randomized controlled studies. These supplements will be used together for the purposes of this research aim, which prioritize efficacy of the glp-1 manipulation over an investigation of any particular supplement. Effective doses of each supplement have been chosen which have been shown to be safe and tolerable for human subject research in prior studies [52, 80, 81]. Aspartame (Equal®) was chosen as a placebo based on prior research indicating that non-nutritive sweeteners are unlikely to stimulate GLP-1 release [82, 83].

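### As written, venous blood for GLP-1 goes on dry ice before it is centrifuged, which would freeze and haemolyse it and make the plasma GLP-1 values unreliable

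*Combined protocol and SAP*

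**What the plan says.** Section 4.3 (Blood sampling) describes blood taken at baseline and 45 minutes after the supplement, to see what the supplement does to circulating GLP-1. It then says "Blood samples will be immediately placed on dry ice and centrifuged the same day", followed by "Extracted plasma will be stored at -80° C". On the tube it says "Blood samples will be collected in a 2mL vacutainer pretreated with a DPP-4 inhibitor in accordance with manufacturer guidelines", and on the assay "Blood samples will be processed in duplicate with the MILLIPORE Glucagon-Like Peptide-1 (Active) ELISA kit".

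HMGB1 comes later in the same paragraph, as a different specimen: "HMGB-1 will be measured at three timepoints via a fingerprick blood sample". Its assay sentence is "Plasma samples will be processed in duplicate using a deproteinization kit and the HMGB1 ELISA kit". No cooling or centrifugation step is attached to the fingerprick blood specifically.

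Section 3 lists as an Aim 4 outcome "Blood plasma GLP-1 levels samples during lab sessions via venipuncture before and after supplement administration", alongside the alcohol-specific satiety questionnaire. Section 4.1 gives the purpose of the two venous samples per session as confirming GLP-1 levels. In section 8.1 the only analysis given for Aim 4 is a repeated measures ANOVA on alcohol-specific satiety.

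**The concern.** Separation has to come before freezing, and the text puts it after. Blood cells rupture when whole blood is frozen and thawed, and their contents pass into what is later spun off as plasma. The written instruction would therefore degrade every GLP-1 sample, and a sample lost this way cannot be recovered after the visit.

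The GLP-1 values matter for interpretation as well as being an outcome. Suppose the supplement shows no effect on satiety. A sound GLP-1 change would help tell a supplement that did not raise GLP-1 from a GLP-1 rise that did not affect satiety. With unreliable GLP-1 values the two explanations cannot be separated.

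**Working it through.** The plan gives no figure on this point, so there is nothing to reproduce. The check is of the order of steps, of which specimens the sentence covers, and of how many samples that is.

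**1. Order of steps (section 4.3, Blood sampling).**
- Step one: dry ice, immediately.
- Step two: centrifugation, at some time on the same day.
- Step three: the extracted plasma goes to -80 C.

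Plasma first appears at step three, so the material at step one is whole blood. No earlier separation, wet-ice or thawing step appears anywhere in the document, and there is no rule for haemolysed specimens.

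**2. Temperature.** Assumption from general laboratory knowledge: dry ice is at about -78 C. That is within about 2 degrees of the -80 C that the plan uses for frozen plasma storage. A 2 mL tube left on it freezes and must thaw before it can be spun.

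**3. Which specimens.** The sentences around the dry-ice instruction concern the baseline and 45-minute draws, the 2 mL tube with DPP-4 inhibitor and the active GLP-1 ELISA. All of these are the venous GLP-1 samples. The fingerprick sample is introduced afterwards with its own assay. That HMGB1 is measured in plasma shows that some separation is intended, but not how or when.

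**4. Counts.** Inputs: 42 expected completers (section 4.2, Participants); 2 laboratory visits; 2 venous and 3 fingerprick samples per visit (section 1.2).
- Venous, directly covered: 42 x 2 x 2 = 168.
- Fingerprick, covered only if the sentence is read to include them: 42 x 2 x 3 = 252.
- If all 55 consented participants gave samples at both visits, the counts would be 55 x 2 x 2 = 220 and 55 x 2 x 3 = 330.

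**5. What depends on the venous samples.** The GLP-1 outcome of Aim 4 and the confirmation that the supplement worked depend on them. The section 8.1 ANOVA for Aim 4 is on satiety scores and does not use GLP-1. Aims 1 to 3 rest on TAC, BrAC, questionnaires and tasks.

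**The case against.** The best defence is that this is a slip of wording. Blood that is to be centrifuged must be liquid, so wet ice was probably meant. The tube is to be used according to the manufacturer's guidelines, and section 9.1.8 refers to written SOPs that may say something different. The study is a pilot. Handling is the same in both counterbalanced conditions, so nothing here shows a bias between supplement and placebo. The tube also contains an inhibitor specified for collecting active GLP-1.

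Most of this is fair, but it does not cure the sentence. The document never mentions wet ice. The reference to manufacturer guidelines is attached to the tube and its inhibitor, not to cooling. The SOPs are not part of the document, and staff would be working from an instruction that says dry ice. The inhibitor does not address rupture of the cells. The point about bias stands: what can be claimed is unreliable values, not a distortion in a known direction.

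A reader might go further in three ways that the text does not support:
- **That HMGB1 is lost as well, making 168 + 252 = 420 affected samples.** Of these, 252/420 = 60% come under the sentence only by inference from the shared paragraph heading. What is documented for the fingerprick samples is a missing handling procedure.
- **That valid GLP-1 values cannot be obtained at all.** The document gives no data on how this ELISA performs in haemolysed samples, so neither the size of the error nor total loss can be asserted.
- **That the supplement comparison in Aim 4 fails.** The planned test is on satiety and makes no use of GLP-1.

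**Conclusion.** The handling sentence is wrong as written and should be corrected. Followed literally, it would freeze and haemolyse the venous GLP-1 blood: 168 samples if 42 participants complete. The plasma GLP-1 outcome of Aim 4, and the evidence that the supplement raised GLP-1, would be unreliable. The satiety ANOVA and Aims 1 to 3 are unaffected.

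For HMGB1 (Aim 5) the conclusion is conditional. If the sentence is meant to cover the 252 fingerprick samples, lysis would release an intracellular protein into the sample, and the measured level would partly reflect cell damage. If it is not, the plan leaves the cooling and separation of those samples unstated. The text needs an addition either way.

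The conclusion rests on the order of steps in section 4.3, which is explicit, and on two pieces of general laboratory knowledge: the temperature of dry ice and the effect of freezing whole blood. It does not depend on any sample size or power figure.

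**What to change.** In section 4.3 (Blood sampling), replace the dry-ice sentence with wording such as:

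*Blood samples will be kept chilled but unfrozen (e.g. on wet ice), centrifuged within the time limit in the tube or kit instructions, and the separated plasma then aliquoted and frozen on dry ice or at -80 C.*

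Add one sentence stating that fingerprick samples for HMGB1 are likewise not frozen before the plasma is separated. Any SOP on specimen handling should be brought into line.

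Recording the time from draw to spin and flagging visibly haemolysed samples would be useful additions, but the correction does not depend on them.

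The cost is two sentences of protocol text, with no new equipment, visits or participants. The one practical downside is that samples must be spun during the visit and cannot be batched at the end of the day.

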Participants will receive a beverage containing either a dietary supplement (10g Fibersol®-2 mixed with water and aspartame sweetener for taste + 725mg decaffeinated green tea extract capsule) or a calorically matched placebo supplement (Aspartame sweetener mixed with water + aspartame capsule) counterbalanced at two separate visits. Forty-five minutes after the dietary supplement, the second blood sample is taken. Next, a priming drink (calculated to achieve 30mg% BAC) is administered to stimulate craving for alcohol [66, 67]. Drinks will consist of 40 proof vodka and a sugar-free cranberry juice mixer at a 1:5 ratio. Doses are calculated to achieve target BACs based on sex and body weight using formulas established in prior research [68]. Fifteen minutes after the priming drink, a novel alcohol-specific satiety questionnaire will be administered followed by alcohol incentive motivation tasks (alcohol purchase task; APT [69], dot probe attentional bias to alcohol-related stimuli), additional validated alcohol subjective response questionnaires (Drug Effects Questionnaire; DEQ[70], Biphasic Alcohol Effects Scale; BAES [71], Alcohol Urge Questionnaire; AUQ [72], Subjective Effects of Alcohol Scale; SEAS [73]), *hunger, fullness, and satiety* visual analogue scale (VAS) items, a BACtrack S80 BrAC measure, and a fingerprick blood sample.

Alcohol-specific satiety paced drinking procedure

Then over a 2-hour period, 5 additional mini-drinks (calculated to achieve an estimated BAC increase of 10mg% each or placebo) are administered with 15 min absorption time between each drink to reach an estimated maximum BAC of 60-70mg%, reflecting a moderate level of alcohol exposure (80mg% is the conventional cutoff for “binge” exposure). Participants have 3 minutes to finish each drink (Average volume of a drink, alcohol+mixer at a 1:5 ratio is 8/5oz for a man/woman). This paradigm is designed to approximate a natural drinking pace, while controlling for the BAC during subjective satiety assessment. The control session will control for expectations of increased satiety with subsequent drinks. Control drinks contain cranberry juice with an alcohol mask (rim sprayed with vodka) matched in total volume to the alcohol drinks. Participants will be told that all drinks contain alcohol. Subjective response questionnaires are repeated 15 minutes after each drink. BACtrack S80 BrAC measures are repeated every 15 minutes.

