After the paced drinking procedure, a final fingerprick blood sample will be taken and participants will remain in the lab until their BAC reaches 0mg% at which point they will be either dismissed. At the end of the second lab session, participants will receive instructions on using the Skyn and BACtrack S80 devices, using the Skyn app for syncing Skyn data and the LifeData app for completing drinking bout EMA surveys and morning surveys about past day alcohol use and consequences.

Remote assessment

During the 7-day naturalistic study, participants will be asked to wear the Skyn for 24 hours/day for 7-days (except when bathing or swimming). On days when participants choose to drink they will initiate drinking bout surveys via smartphone by indicating they have started drinking, after which they will be prompted to provide a BrAC reading once every 20-minutes throughout the drinking bout and for up to 1-hour after the drinking bout ends. Every 60-minutes participants will also self-report alcohol amount and subjective intoxication during the drinking bout. Importantly, participants will be informed that they are not expected to change their drinking behaviors during the study and compensation is not contingent on self-reports or breathalyzer readings during drinking bouts. Participants will complete daily morning surveys about past day alcohol use and consequences and evening surveys about daily pain and stress.

After the 7-day protocol, participants will return their devices to the PI's lab and report past 7-day drinking behaviors (timeline follow-back; TLFB) and drinking consequences (Brief Young Adult Alcohol Consequences Questionnaire, Importance of Consequences of Drinking short-form) and undergo a DEXA scan. Participants will be compensated upon device return with up to \$240 (\$20 for baseline surveys, \$50 for lab visit one, \$50 for lab visit two, \$70 for all 7-day EMA study procedures, \$10 for device return, \$10 for follow-up questionnaires, \$10 for DEXA scan, and \$10 study completion bonus).

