BACtrack Skyn TAC Monitor: The BACtrack Skyn is a small, lightweight wrist monitor that measures alcohol exposure through the 1% of alcohol transmitted through perspiration (i.e., transdermal alcohol concentration). The device wirelessly syncs to the Skyn app on the participant's iPhone to collect TAC data every 20 seconds. Alcohol exposure is detected with an average delay of 35.6 minutes [84]. The following outcomes are derived from TAC data: *drinking intensity* (peak TAC and area under the curve [AUC]), *drinking duration* (hours with TAC >0 µg/L air), *rise rate* (average rate of all ascending point-to-point TAC values), and *fall rate* (average rate of all descending point-to-point TAC values).

BACtrack S80 BrAC Monitor: The BACtrack S80 is a portable, battery-operated professional breathalyzer that measures the percentage of alcohol in a person's breath (i.e., BrAC). Participants capture BrAC within seconds after following a series of automated instructions provided by the S80 and breathing into the mouthpiece. Participants will report their S80 readings in the EMA surveys. The outcomes derived from the BrAC data are the same as those described above for TAC data.

Behavioral tasks:

The alcohol purchase task (APT) measures the hypothetical behavioral economic demand for alcohol at 14 different price points. This measure is sensitive to the reinforcing effects of alcohol, and predictive of real-world alcohol consumption [69]. The following outcomes are derived from the APT: APT-intensity (consumption when drinks were free); APT-breakpoint (the first price at which consumption was suppressed to zero); and APT-Omax (maximum alcohol expenditure) [69]. The task takes no more than 5 minutes to complete and is administered on REDCap

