8. STATISTICAL CONSIDERATIONS

8.1 SUMMARIZE THE STATISTICAL ANALYSIS STRATEGY FOR EACH SPECIFIC AIM

Descriptive statistics (e.g., frequency, mean, standard deviation, variance, range) will be generated for all study variables. Continuous study variables will also be examined for normality and homogeneity of variances using visual inspection methods (e.g., histograms, box plots, residuals, Normal Q-Q plots) and quantitative methods (Shapiro-Wilk test). If these assumptions are violated, the continuous study variables will be transformed, as necessary (e.g., log transformation). Exploratory analysis of the association between participant characteristics and study outcomes will be tested using Pearson correlation coefficients, chi square, and analysis of variance.

To analyze study aims 1 and 2, multi-level regression models will examine the within-person correlations between TAC and BrAC measurements, including peak TAC/BrAC and area under the TAC/BrAC curves (AUC). Models will test within-person correlations between TAC and BrAC during the in-lab alcohol administration and naturalistic drinking bouts and will investigate whether correlations differ across conditions. Multi-level models will test TAC predicting drinks consumed and the odds and frequency of alcohol-related harms (e.g., hangover, missed classes), and will examine whether BrAC accounts for additional variance in those outcomes. Person-specific algorithms for predicting BrAC from Skyn TAC data will be developed using a backwards step-wise multiple linear regression approach starting with Skyn TAC data as the primary predictor and adding relevant covariates (e.g., fat-free mass, skin temperature) that result in statistically significant and/or clinically meaningful improvements to the model.

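### TAC rise and fall rates, averaged over all upward or downward steps of 20-second data, are open to domination by rapid noise or rounding and are not like for like with BrAC rates taken at 15 or 20 minutes

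*Combined protocol and SAP*

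**What the plan says.** The Skyn monitor paragraph of section 4.3 says the device syncs "to collect TAC data every 20 seconds". It lists rise rate, the "average rate of all ascending point-to-point TAC values", and fall rate, the "average rate of all descending point-to-point TAC values", among the outcomes derived from TAC, alongside peak, AUC and duration.

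The S80 paragraph that follows adds: "The outcomes derived from the BrAC data are the same as those described above for TAC data". The BrAC schedules differ from the TAC schedule and from each other. In the laboratory, "BACtrack S80 BrAC measures are repeated every 15 minutes". In the field, participants are "prompted to provide a BrAC reading once every 20-minutes throughout the drinking bout and for up to 1-hour after the drinking bout ends".

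Section 8.1 describes the within-person TAC and BrAC correlations as "including peak TAC/BrAC and area under the TAC/BrAC curves (AUC"; it does not name rise or fall rate. Neither section gives a filter, an averaging window, a minimum step, a common time grid, or a rule that restricts rises to the period before the peak and falls to the period after it.

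**The concern.** An upward flicker during elimination counts as a rise, and a downward flicker during absorption counts as a fall. Over 20 seconds the true change is very small, so a small error in each reading can outweigh it. The same formula applied to BrAC uses steps 45 to 60 times longer, where the true change is much larger relative to the error. The two sets of rates would share a name but respond differently to noise.

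Two of the listed outcomes are at stake. If the raw signal carries rapid noise, TAC rise and fall rates would be similar to each other and weakly related to how fast alcohol rises or falls. A weak association with BrAC rates or with harms could then reflect the formula and not the sensor.

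**Working it through.** The plan states no numerical result for these rates, so there is no figure to reproduce.

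**Inputs from section 4.3.** TAC every 20 s gives 3600/20 = 180 steps per hour. One BrAC step spans 15 × 60/20 = 45 TAC steps in the laboratory and 20 × 60/20 = 60 in the field.

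**Assumed inputs.** Noise level, resolution and curve shape are not in the documents. Noise SD *s* is shown over a range, as a percentage of a peak of 100 units.

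**Analytic result.** With independent noise of SD *s*, the difference of two readings has SD √2·*s*. The mean of its positive half is √2·*s* × √(2/π) = 2*s*/√π = 1.128*s*. At 180 steps per hour this is 203*s* per hour, whatever the kinetics. It equals a true rise of 40 per hour when *s* = 40/203 ≈ 0.2, that is, 0.2% of peak.

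**Simulation of the formula at 20 s.** Smooth curve, 2.5 h rise and 4 h fall, so true rates are 100/2.5 = 40 and 100/4 = 25 per hour:

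| Noise SD, % of peak | Rise | Fall |
|---|---|---|
| 0 | 40 | 25 |
| 0.1 | 39 | 33 |
| 0.2 | 51 | 49 |
| 0.5 | 105 | 105 |
| 1 | 206 | 205 |
| 2 | 407 | 410 |
| 5 | 1015 | 1021 |

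A separate linear curve (2 h rise, 4 h fall, true 50 and 25) gives 106/105 at 0.5%, 205/205 at 1% and 408/407 at 2%.

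**Other kinds of error.** At 1% of peak, autocorrelated noise with a 5-minute time constant gives 60/58 on the linear curve (true 50/25). With a 15-minute constant the smooth curve gives 43/40 (true 40/25), rising to 154/153 at 5%. Rounding to 1% of peak, with no random noise, gives 180/180, because the smallest non-zero step is 1 unit × 180 per hour.

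**Correlation with BrAC.** In 400 simulated bouts (peak 40–160, rise 1–4 h, fall 2–6 h, BrAC noise SD 1 unit), the 20-second TAC rise rate was correlated with the 20-minute BrAC rise rate. TAC noise is in units where 1 is 1% of a peak of 100.

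| TAC noise SD | Same noise for all | Noise varying between bouts (log SD 0.3) | Varying noise, TAC sampled every 20 min |
|---|---|---|---|
| 0 | 0.98 | 0.98 | 0.98 |
| 0.1 | 0.93 | 0.93 | 0.99 |
| 0.5 | 0.73 | 0.18 | 0.98 |
| 1 | 0.42 | 0.05 | 0.98 |
| 2 | 0.08 | −0.04 | 0.96 |
| 5 | −0.08 | −0.06 | 0.90 |

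**Effect of averaging onto the grid.** A 20-minute mean of 60 readings divides independent noise by √60, and the step is 60 times longer. The noise term falls by 60 × √60 ≈ 465, from 203*s* to about 0.44*s* per hour. On the linear curve the existing formula then gives about 44/25 at every noise level tested. The 44 is flattening at the peak: five steps at 50 and one at 12.5 give (5 × 50 + 12.5)/6 = 43.75.

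**Where the TAC record ends.** Field BrAC stops at most 60 minutes after the bout, about 60/20 = 3 readings. Section 4.3 gives an average TAC delay of 35.6 minutes. Assume the delay is a pure shift and BrAC peaks at the end of the bout. TAC then has 60 − 35.6 = 24.4 minutes of falling limb before the last BrAC reading. If TAC is cut there, its noise-free fall rate on the 20-minute grid is undefined, 1.7 or 6.9 per hour for rises of 1, 2 and 3 hours, against a true 25. Using the full TAC record gives 22–24.

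**The case against.** The strongest reply is that the size depends on quantities the documents do not contain. With no noise the definition returns the true rates exactly. Independent error at every 20-second reading is the harshest case for this formula. The text also does not say that the values are unprocessed; silence about filtering is not a plan to skip it. All of this stands.

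A reader might infer that these outcomes measure sensor jitter instead of alcohol kinetics, or that they cannot be compared with BrAC at all. The documents support neither statement. Correlation does not need equal units or intervals, and it remains at 0.93 or above at the lowest noise levels tested.

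A reader might also infer that the test of the sensor in Aims 1 and 2 is undermined. Section 8.1 names peak and AUC for the TAC and BrAC correlations, and no analysis described there depends expressly on the rates. Its wording leaves room for other metrics, and section 4.3 lists the rates as derived outcomes, so they are not irrelevant, but the exposure is confined to them. The study also describes itself as gathering pilot data.

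The reply does not remove the point. Section 4.3 states a working rule, classification by sign on 20-second data, and that rule is sensitive to small, rapid error or coarse rounding. If the sponsor already smooths the readings, one sentence would largely settle the noise question; the time grid and the extent of the curve would still need stating.

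**Conclusion.** The point holds in conditional form. As defined, TAC rise and fall rates are open to domination by rapid noise or rounding and are not like for like with BrAC rates. With independent noise, the artefact matches a true rise of 40 per hour at about 0.2% of peak and makes rise and fall nearly equal from about 0.5%. Noise with a 15-minute time constant has a much smaller effect at 1% of peak, and a smooth or filtered signal has none.

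These sizes rest on assumed curves and noise, because the documents give no sensor noise, resolution or processing step. The 203*s* term needs only independent, normally distributed error and no curve shape. The point concerns two derived outcomes and makes no claim about peak or AUC.

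**What to change.** In the Skyn monitor paragraph of section 4.3, state that TAC is averaged onto the BrAC grid (15 minutes in the laboratory, 20 minutes in the field) before the existing rise- and fall-rate formula is applied to both TAC and BrAC. State also that TAC rates use the full TAC curve of the bout and are not cut at the last BrAC reading. Note that the field BrAC fall rate needs cautious interpretation, because readings stop at most 1 hour after the bout.

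Do not replace the formula with slopes from first value to peak and from peak to the last common reading. In the field, the 35.6-minute delay and the early end of BrAC would give the undefined or far too low TAC fall rates shown in the working.

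The change needs a few lines of code and no new data. Detail below 15 to 20 minutes is lost, and steep rises are flattened: about 44 for a true 50 per hour, and 56 for a true 100 per hour with a 1-hour rise and the 35.6-minute delay.
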